10.2 Secondary study parameter(s)

Secondary study parameters are patient satisfaction and definition of a set of metrics for evaluation of efficacy of the BCI system for a larger clinical trial.

In the case of unreliable communication at the time of inclusion, secondary study parameters can only be investigated if the patient can use the UNP system to communicate reliably.

Patient satisfaction

This will be measured with standardized questionnaires and pattern of unsupervised use.

Quality of life

We assess the quality of life of the patient throughout the study. The so called Anamnestic Comparative Self-Assessment (ACSA) will be used for this assessment (Bruno et al., 2011), whose biographical +5 and -5 scale anchors the patient's memories of the best period in their life and their worst period ever. The first (presurgical) test serves as baseline measure. The test will be repeated five times after the implantation of the electrodes, in order to monitor whether quality of life changes over time ([See Sections 15.4 and 8.3.10](#)).

The effects of the BCI on quality of life

The PIADS ([Section F1.9](#)) is used to estimate the effects of device on the quality of life. PIADS (piads.net) is a 26-item, self-rating questionnaire that is designed to measure a person's perceptions of how assistive devices affect quality of life. For each of the 26 items, patients have to indicate (on a 7-point scale) whether this aspect of life has increased or decreased. The test will be performed four weeks after the implantation and is repeated every 12 weeks until the end of the study, in order to study changes over time.

Importance of Device Aspects and User Satisfaction

The opinion of the patient about the importance of a range of aspects of the device will be determined using a dedicated questionnaire. The patient will rate each item on a four point scale that ranges from 'not at all important' to 'very important' ([See Section F1.8A](#)). The test will be performed presurgically, and repeated at the end of the study to monitor any changes. At the end of the study, user satisfaction with the BCI will be measured using a list of specific items (the same items as in the 'Importance of Device Aspects questionnaire'), that will be rated by the patient on a four point scale that ranges from 'not satisfied at all' to 'very satisfied' ([See Section F1.8A+B](#)).

Pattern of Use

The Brain Interpreter receives and stores all data from the streaming unit continuously, including start time and parameter settings and including data from electrodes not used for control.

States that are logged are:

- idle or active mode, activated by caretaker or patient

Events that are logged are:

- all events that are classified as an intent to use the switch, also in idle mode
- caretaker starting or stopping active and idle mode
- patient going in or out of idle mode.

Using this information, the number of times per day a patient uses the system for training or real communication will be determined, as well as the duration of each session.

Definition of a set of metrics for evaluation of efficacy of the BCI system for a larger clinical trial

Throughout the study, we will assess experimental parameters for a larger clinical study, including decoding algorithms, sample size, augmenting and prohibitive factors affecting BCI performance, factors affecting use of the system and indices of evaluation. This can only be investigated with chronically implanted systems, hence the present pilot study. All data collected during the visits of the research team to the patient can be used to assess these parameters. In addition, data acquired during the EEG measurement session will be used to address this study parameter. EEG data will be analyzed offline with standard programs for signal processing or custom programs. All data are converted to frequency space, and band pass filters are applied to generate multiple traces of power in specific bands (standard procedure). Of primary interest are theta (3-7 Hz) and mu/beta (7-28 Hz) bands. We will evaluate baseline spectral power as well as the ability of the participant to modulate power during the localizer tasks. Data will be compared with ECoG features and the fMRI activation pattern and will provide information about whether or not EEG measurements may be used to assess if certain individuals are more or less likely to generate high-amplitude changes in spectral power.

10.3 Other study parameters

fMRI activation pattern

fMRI data are analyzed with SPM8. The analysis parameters are the same as those that are used routinely for clinical fMRI data analysis as performed at the UMC. Briefly, fMRI scans are registered to the first scans, and then to the anatomical scan. Further analyses are performed in native space (not in a standard space such as MNI) so that the activity maps can be used during surgery. For the latter, the fMRI map superimposed on the native anatomy is co-registered with the patients head based on the fiducials or bone screws (see Section 8.3.3). For fMRI statistical analysis we use a General Linear Model multiple

regression analysis. The factor matrix includes a set of cosine waveforms acting as a high-pass filter to reduce random noise. The factors of interest depend on the task, but will correspond to the task designs, with brief (mental calculation) or standard epochs (motor imagery/attempt) corresponding to a block design. This method has been used in all the preceding research on intracranial BCI at the UMC Utrecht. Factor loadings (beta's) are converted to t-values, which make up the fMRI t-maps for each function (cognitive control, and motor imagery/attempt). Given our extensive experience with individual t-maps for clinical fMRI scans for neurosurgery, we will not apply a fixed cutoff for significance, but we will identify the peak t-values within predefined Regions of Interest. These are the border region between left hemisphere F1 and F2 (Brodmann areas 9 and 46) for cognitive control, and left premotor and motor region (Brodmann area 6 and 4) for motor imagery/attempt. Based on the patterns of activity around the peak values, the exact location and orientation of the 4 electrode strips is determined..

ECoG activation

ECoG data are analyzed with programs for signal processing or custom programs written in, for example Matlab, a platform for ECoG and fMRI research. Analysis involves offline and online processing. Offline processing is conducted for investigation of the full extent of data feature space to find optimal parameter settings for detecting brain activity. For this, tasks are imposed on the patient and correlations are sought between electrodes and tasks (similar to fMRI paradigms). First, data are converted to differential signals. Since the device can only create pairs within a strip, we have 6 possible pairs within each strip of 4 electrodes. Next, all data are converted to frequency space, and band pass filters are applied to generate multiple traces of power in specific bands (standard procedure). Next, for each trace the r-squared is calculated (similar to correlation value). Significant r-squares are then compared for low and high frequency bands. Of primary interest are theta (3-7 Hz) and gamma (50-100 Hz) bands for cognitive control, and mu/beta (7-28 Hz) and gamma (50-100Hz) bands for imagery/attempt, based on prior research, but specific frequencies are determined for each electrode pair and each individual separately based on r-squared values. Significance thresholds are $p < 0.05$, Bonferroni-corrected for the number of electrode pairs (12 per function). During training, intention of the patient is detected using a linear summation of the signal features, followed by classification using a threshold. Finally, a machine learning algorithm is applied to the selected electrode pairs and frequency bands to build support vector machines for later online classification. Real-time ECoG data processing will not involve statistical testing. The selected frequency bands and electrode pairs are used, with classifiers that are based on the support vector machines determined in offline analyses. Classification is performed in real time, with parameter settings for conversion to a switch signal ([Section 8.3.9](#)).

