After the first surgery the best electrode strips will be identified during a two day screening period before the second surgery. The two day screening period can be prolonged up to 7 days dependent on patient condition and quality of electrode selection screening results. The patient is asked to perform a maximum of eight total hours of testing each day. The duration of each test and the duration between tests are subject to patient condition. All 16 implanted electrodes ([see Section 5](#)) are connected to the clinical Micromed intracranial EEG system. The data will be acquired in the time domain (512Hz sampling rate, 22bit). The data will be recorded for 24 hours every day. Cognitive control and motor imagery/attempt localizer tasks are performed (described below). These are similar to the tasks that the patient has performed in the 3T scanner. The patient gets no feedback on his brain activity. Based on this data the best electrode strips are determined. If the results of the motor tasks indicate that different hand / finger movements show different activation patterns in the sensorimotor strips, we will connect two of the three sensorimotor strips to the device in the second surgery. If the results of the motor tasks indicate overlap between the activations of the different hand/finger movements, one motor strip will be connected, as well as the dlpfc strip. The final decision of electrode strip selection will be made by the Principal Investigator before the second surgery. The Principal Investigator may decide at this time not to proceed with the second surgery if electrode selection is not possible.

During the second surgery

After the Activa PC+S is in place and the electrodes are connected, proper functioning of the Activa P+S is ensured. The Activa PC+S will be configured and the signal quality will be tested using the Sensing Programmer and the SPTM ([see Section 5.1.1](#)). Signal quality is tested by reading the time domain data. The Principal investigator will be responsible for evaluating the correct functioning of the Activa PC+S.

Analysis of localizer task data (after first surgery)

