For all channel combinations within a strip the bipolar reference is computed (this leads to six bipolar channels for each strip) for the localizer tasks. The data is epoched and the power is computed for all frequencies between 1 and 120Hz. For each bipolar channel the correlation with the task (expressed as the R^2 value) is computed. The channels that show a significant R^2 value are considered possible candidates for BCI control. Channels that show a significant change in power over a broad band of frequencies (preferably between 65Hz and 95Hz) are favored. This procedure is repeated for all repetitions of the localizer task. The two channel pairs that show a consistently high R^2 are selected for being connected to the device. Based on previous experiments with epilepsy patients an R^2 of above 0.3 will be considered sufficient. This analysis is carried out by members of the Research Team.

Localizer tasks used (after first surgery)

The signal for controlling the Assistive Technology device will be generated either by cognitive control or by motor imagery/attempt. For both functions localizer tasks similar to those performed in the FMRI scanner are performed. We describe the ECoG localizer versions of the tasks here.

Localizer task - Cognitive control

In this task the patient has to count forward (in steps of one), count backwards (in steps of seven, or less depending on the abilities of the patient) or relax. Each condition starts with an instruction ('tel vooruit', 'tel terug', 'rust'), for the two counting conditions a start number is given. For the count forward condition a number below 10 is shown, for the count backward condition a number above fifty is shown. Each trial last 15 seconds followed by an inter-trial interval of 2 seconds in which a fixation cross is shown. The entire task lasts about 9 minutes. The patient will get the following instruction:

"Je ziet straks 3 verschillende instructies. Bij 'rust' hoef je niets te doen. Bij 'tel vooruit' ga je vooruit tellen vanaf het getal dat in beeld verschijnt, in stappen van 1. Bij 'tel terug' ga je terug tellen vanaf het getal dat in beeld verschijnt, in stappen van 7. Het duurt ongeveer 9 minuten."

Localizer task - Mental imagery of the left and right hand

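### The Bonferroni divisor of 12 pairs per function in 10.3 names no stage and does not fit strip selection with three motor strips and one prefrontal strip

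*Combined protocol and SAP*

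**What the plan says.** Section 10.3 (ECoG activation) describes an offline analysis in which "correlations are sought between electrodes and tasks". It notes that "we have 6 possible pairs within each strip of 4 electrodes" and sets the significance threshold at p < 0.05, "Bonferroni-corrected for the number of electrode pairs (12 per function". It does not say whether this applies to strip selection, to the analyses after connection, or to both.

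Section 8.3.7 describes strip selection between the two surgeries. "All 16 implanted electrodes" are recorded. Bipolar channels are formed within strips ("this leads to six bipolar channels for each strip"), and channels with a significant R-squared "value are considered possible candidates for BCI control". An R-squared "of above 0.3 will be considered sufficient". No p-value threshold appears there.

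On the layout, sections 5.1.1, 8.3.3 and 8.3.6 place three strips over motor cortex and one over dorsolateral prefrontal cortex (DLPFC), and 8.3.7 speaks of three sensorimotor strips. The closing paragraph of 15.5 and Checklist Procedures 1 in 15.6 still give two strips for each function.

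**The concern.** At six pairs per strip, 12 per function implies two strips per function. That is the layout left in 15.5 and the checklist, not the one now to be implanted. Section 10.3 is the only place that gives a threshold for the significance test that 8.3.7 uses to name candidate channels. If it governs that step, the divisor is too small for motor pairs and too large for prefrontal pairs. It then tilts between the two functions just before the team decides which strips to connect in the second surgery.

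The checklist raises a separate record-keeping point. For a three-plus-one implant, neither strip-count box can be ticked truthfully, and the motor part has no label or location line for a third strip.

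**Working it through.** **Inputs.** Alpha 0.05 and divisor 12 (10.3); four electrodes per strip (5.1.1) and six pairs per strip (8.3.7, 10.3); three motor strips and one prefrontal strip (5.1.1, 8.3.3, 8.3.6).

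**The plan's figure.** Pairs per strip = C(4,2) = 6. Two strips give 2 × 6 = 12, so the stated divisor is reproduced, with a threshold of 0.05/12 = 0.0042.

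**Pair counts at strip selection.** Motor 3 × 6 = 18; prefrontal 1 × 6 = 6; all four strips 4 × 6 = 24. None is 12.

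**Pair counts after connection.** Two strips are connected, so there are 12 pairs in all. Twelve is right for two motor strips, and for any task tested on both connected strips. With one motor and one prefrontal strip, each tested only on its own task, it is 6 per function.

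**Familywise error over pairs at a = 0.05/12.** The Bonferroni bound is k × a. If tests were independent, the rate would be 1 − (1 − a)^k. Pairs within a strip share electrodes, so the independent figure is only indicative.

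| Pairs k | Threshold 0.05/k | Bound at 0.05/12 | If independent |
|---|---|---|---|
| 6 | 0.0083 | 2.5% | 2.5% |
| 12 | 0.0042 | 5.0% | 4.9% |
| 18 | 0.0028 | 7.5% | 7.2% |
| 24 | 0.0021 | 10.0% | 9.5% |

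**When the divisor can change a decision.** The critical R-squared is t²/(t² + n − 2), with t the two-sided critical value on n − 2 degrees of freedom and n the number of epochs. Sidedness is not stated, so two-sided is an assumption.

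| Epochs n | 0.05/6 | 0.05/12 | 0.05/18 | 0.05/24 |
|---|---|---|---|---|
| 21 | 0.313 | 0.358 | 0.383 | 0.400 |
| 26 | 0.256 | 0.295 | 0.316 | 0.332 |
| 28 | 0.239 | 0.275 | 0.296 | 0.310 |
| 30 | 0.224 | 0.258 | 0.278 | 0.291 |
| 31 | 0.217 | 0.250 | 0.269 | 0.283 |
| 63 | 0.109 | 0.127 | 0.137 | 0.145 |

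The 0.3 rule becomes the stricter one from 26 epochs at 0.05/12, from 28 at 0.05/18 and from 30 at 0.05/24. Beyond that point the divisor makes no difference.

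**How many epochs there are.** Epoch length is not given. In the counting and hand tasks, "Each trial last 15 seconds followed by an inter-trial interval of 2 seconds", and a run lasts about 9 minutes, so there are 540/17 = 31.8 trials over three conditions. With one epoch per trial:

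- Two of the three conditions give about 21 epochs (31.8 × 2/3 = 21.2). The p-threshold then exceeds 0.3 for every divisor, so it binds.
- Both active conditions against rest give about 31 epochs. The 0.3 rule is then stricter for every divisor.

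Three epochs per trial in the two-condition contrast would give 63, and the divisor is irrelevant. The finger task gives no trial timing.

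**The case against.** The strongest defence is that 12 may be meant for the stage after connection. Section 10.3 counts the pairs that the device can create and leads on to training and online classification. The device carries two connected strips. The research visit checklist in 15.4 lists exactly 12 pairs for the impedance check and includes both motor and working-memory localizers. If each task is tested on every connected pair, 12 per function is correct in either connection configuration. It is also correct for participants with an existing implant on two sensorimotor strips, who skip strip selection. This stands: a reader might infer that 12 is wrong throughout, and the documents do not support that.

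Second, applying 10.3 to strip selection is an inference. Section 8.3.7 does not cite it, and the processing differs: all frequencies from 1 to 120 Hz in 8.3.7, band-filtered traces in 10.3. The inference is reasonable, since no other threshold is given, but it remains an assumption.

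Third, a reader might take 7.2% or 9.5% as the true error rate of selection, and the new divisor as restoring 5%. Neither follows. The figures count pairs only, while frequencies are also chosen per pair from r-squared values. As an illustration, with two independent bands, 18 pairs at 0.05/18 give 1 − (1 − 0.05/18)^36 = 9.5%.

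Fourth, it is tempting to say that the wrong strips would be connected or leads confused. Ranking by R-squared does not depend on the divisor. Selection also needs consistently high R-squared over repetitions, a judgement on whether hand and finger patterns differ, and the Principal Investigator's decision. Lead identity is also secured by marked ligatures, the study coordinator's notes and the CT rendering.

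**Conclusion.** The point holds as a minor inconsistency. The divisor does not name its stage and does not fit strip selection under the current layout. If the 10.3 threshold governs 8.3.7 and each function is tested on its own strips, 0.05/12 allows a pair-only familywise error of up to 7.5% for motor and holds prefrontal to at most 2.5%. If every task is tested on all four strips, the bound is 10%. These are statements about the pair count, not about the whole selection procedure.

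An effect on candidate channels is possible only below about 26 to 30 epochs. In the 21-epoch case, a motor channel with R-squared between 0.358 and 0.383 would pass when it should not, and a prefrontal channel between 0.313 and 0.358 would fail when it should pass. That case assumes one epoch per trial and a two-condition contrast. Section 10 is descriptive and per subject, and the primary endpoint is unaffected. Confidence is high for the pair counts and the leftover two-plus-two text, and lower that 10.3 was meant for strip selection.

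**What to change.** - **Section 10.3.** Replace the fixed 12 by 6 times the number of strips tested for that task at that stage. At strip selection this is 18 motor and 6 prefrontal, or 24 per task if all four strips are tested; after connection it is 6 per connected strip tested. State which strips each task is tested on, and that the correction covers electrode pairs only, not the choice of frequency.
- **Section 15.5.** Change the last paragraph to three motor strips and one prefrontal strip.
- **Checklist Procedures 1 (15.6).** Ask for three motor strips, with label and location lines for strips 1 to 3, and one DLPFC strip, with lines for strip 4.

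This costs a short edit to 10.3, one to 15.5 and one revised form, with no new data and no patient burden. The downside is a slightly stricter motor threshold at selection: a critical R-squared of 0.383 instead of 0.358 at 21 epochs.

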10.4 Interim analysis (if applicable)

After three subjects the results are evaluated. Given that this is a pilot study, we will evaluate progress on an individual basis and make decisions on how to proceed based on achieved levels of BCI control. For details, see [Section 4.4](#) and [Section 8.7](#).

11.ETHICAL CONSIDERATIONS

11.1 Regulation statement

The study will be conducted according to the principles of the Declaration of Helsinki (version 7, October 2008) and in accordance with the Medical Research Involving Human Subjects Act (WMO) and relevant other guidelines, regulations and acts.

11.2 Recruitment and consent

11.2.1 Subject recruitment

Executive Summary

This procedure describes how we will reach possible patients, and how to go about once a patient has shown interest in the study.

Full description of procedures

Patients with locked-in syndrome who may be interested to be included in the BCI study will be identified as follows:

- Patient organizations, Assistive Technology companies, the 'Centrum voor Thuisbeademing', nursing homes, and other institutions and foundations will be approached by letter, with a request to inform potential candidates about the existence of the UNP project, and to provide potential candidates with the UNP information leaflet (see Section E3 for the letter sent to non-physicians).
- One month after these requests are sent out, it will be evaluated whether or not a sufficient number of eligible candidates could be found. If not, health care professionals of various disciplines (e.g. neurologists, general practitioners, rehabilitation doctors, physiotherapists) will be approached by letter with a request to inform the researchers whether or not they have locked-in patients in their practice or file. If they do, the professionals will be requested to approach the respective patients and their caregivers, and ask their permission for approach with information by the researchers (see Section E3 for the letter sent to professionals).
- A second letter will be sent out to "healthcare professionals" who didn't respond to the first letter.
- During the whole recruitment period, whenever possible, the UNP project will be presented by the researchers, e.g. during public outreach, interviews and scientific symposia.
- Four month after recruitment starts, if the number of eligible candidates is insufficient, we will extend recruitment and mention the possibility to participate in the UNP in more media, e.g. newsletters, websites and social media of patient organizations and other organizations related to our patient group. We will actively engage in social media for recruitment. In all of these media we will refer to the multilingual website set up for the UNP study: www.neuroprosthesis.eu (in English) / www.neuroprothese.nl (in Dutch). This website may be translated into other languages. See Section E3 for examples.

Patients/caregivers can contact the research team directly, or they can be contacted by the research team after caregivers have given agreement to their physician. Contact will be made with the patient or caregivers to confirm interest of the patient in the study and to verify that the patient meets inclusion criteria 1-8, and does not meet exclusion criteria 1-5 (see Section F1.1 and Section F1.2). The other inclusion/exclusion criteria will be thoroughly tested after the informed consent procedure. If the patient meets these first criteria, the patient will be visited by members of the research team, who will explain the project in detail. The complete project will be explained verbally to the patient and his/her relatives and/or caregivers and/or legal guardian. This information will include the following:

- the purpose of the research
- the expected duration of the subject's participation
- a description of the procedures to be followed and an identification of all the procedures which are considered experimental
- risks and benefits
- the extent to which confidentiality of records identifying the subject will be maintained

During this visit, the reliability of the patient's communication channel will be verified using a questionnaire (see Section F1.3 and F1.3b). When there is doubt about the patient's ability to communicate reliably the communication test can be repeated. When, the score is repeatedly below the criteria as described in section 11.2.2 the subject will not be included, unless there is evidence of earlier expressions of the will to participate after information was given to the patient (eg legal document).

A written summary of the research project will be provided by the investigator, as well as a letter in which they are formally asked to consider participation in the study (see Section E1.1). The patient is free to decide if he/she will participate in this study. Patients have 2 weeks to consider possible participation. In case of unreliable communication the legal guardian decides on behalf of the patient. The research team will make contact with the patient (or the family) after this period and ask whether the patient is still interested. If the patient is still interested, he will be once more visited by the research team and the project will be again explained verbally. During this visit, one of the neurosurgeons involved in the project will join the researchers. He will explain in detail the medical aspects of the procedure. For patients living abroad, this appointment may be accomplished via a video-call. *

After the explanation, the patient's understanding of the details of the project will be verified using a questionnaire (see Section F1.4). In case of unreliable communication this evaluation will not be possible with the patient, but it will be made sure that the legal representative is fully aware of all details of the study using the same questionnaire. This visit is followed by another, shorter, period of consideration about participation. A few days after this visit, the research team will have telephone contact with the patient (or family) to verify continuing interest in the study. If the patient remains interested and wants to participate, he/she will be visited by a member of the research team and an independent observer for the informed

consent procedure. For patients living abroad, the informed consent procedure will take place at the UMCU.

* For participants with an existing implant, the neurosurgeon will not join during this visit, since the patient will be aware of the medical issues related to the surgery. There will be a meeting with the neurosurgeon shortly before the implantation procedure.

If, during the process before the informed consent procedure, the researchers feel that the communicative abilities of the patient may benefit considerably from existing non-invasive assistive technology (e.g. commercially available dynamic systems, eye trackers etc) that he/she was not aware of before, the patient will be referred to an assistive technology advisor, see the Decision tree in Section 15.8. Considerations about possible inclusion in the current UNP study will be postponed until there is clarity about the alternatives.

In case of two eligible subjects at the same time, the date of the first contact between the patient and the researchers will determine who will be included first, with personal circumstances of the patient being taken into account.

People involved

Research team

Principal Investigator

Responsibilities

The research team will be responsible for contacting the patient and administering the telephone questionnaires. The principal investigator will be consulted once these questionnaires have been filled out, for a decision about inclusion or exclusion of the specific patient. The research team is also responsible for the explanation of the whole project to the patient, the verification of the reliability of the communication channel and the verification of the understanding of the project by the patient during the first visit to the patient. In the case of unreliable communication, the research team is responsible for determining if there is clear indication that the patient and legal guardian understand the protocol and the risks and want to participate (eg legal document), and if their legal guardian agrees to (and signs for) their participation.

